The duration of overall CR is measured from the time measurement criteria are first met for CR until the first date that progressive disease is objectively documented.

Duration of stable disease: Stable disease is measured from the start of the treatment until the criteria for progression are met, taking as reference the smallest measurements recorded since the treatment started, including the baseline measurements.

11. STATISTICAL CONSIDERATIONS

11.1 Study Design/Endpoints

The study is designed as a combined Phase I/II interventional non-randomized single-center study of the safety and efficacy of quinacrine in combination with capecitabine in the treatment of patients with advanced stage colorectal adenocarcinoma.

The primary aims in Phase I are to describe toxicities/adverse reactions of quinacrine treatment in combination with capecitabine in patients with advanced CRC. Simon's accelerated titration 4B design is used to determine the dose for Phase II part of the trial. This trial design will be utilized given that quinacrine has been used in the clinic for many decades. We are not anticipating additional toxicity due to the combination with capecitabine. Total Phase I enrollment will be between 3 and 18.

Figure 3 charts the accelerated titration phase I design. It indicates that at each dose level one patient will be initially treated. If that patient's common toxicity criteria score, T, is at most 2 the next patient is dosed at the next higher level. If the patient's score exceeds 2, two more patients are treated at the same dose level. If these two patients' scores are both at most 2, the next patient is treated at the next higher dose level. If both patients have scores higher than 2, the dose is de-escalated one level. If only one of *Committee 2015 For Chase Career Carter® Office of Clinical Because. All rights rearrand*

the two has a score higher than 2, then 3 additional patients are treated at the current dose level. Finally, if at most 2 patients among the 6 at this dose level have scores higher than 2, this dose is declared the MTD. When the dose is de-escalated, the number of patients treated at the lower dose level is enlarged to 6 by adding 5, if escalation from it was made using only one patient, or by adding 3, if 3 patients have been previously treated with the lower dose. The table below lists the chance of dose escalation, pesc, in terms of the underlying chance that this dose will result in a score, T > 2. For example, if the chance that T will exceed 2 is 30% the chance of escalation is 85%. The table also lists the chance of de-escalation, pdesc, in the same way, and the chance that the MTD will be decided, pstay, on first entering a dose level. The chance that a dose level will be declared MTD when being reached by de-escalation, mtddsc, is listed directly below line listing p (T>2).

	Chan	ce of e	scalatio	on, MT	D in pl	ace or (de-esca	lation		
pesc:	0.981	0.928	0.847	0.744	0.625	0.496	0.363	0.232	0.109	
pstay:	0.013	0.033	0.043	0.041	0.031	0.018	0.008	0.002	0.000	
pdesc:	0.006	0.039	0.110	0.215	0.344	0.486	0.629	0.766	0.891	
p(T>2)	: 0.100	0.200	0.300	0.400	0.500	0.600	0.700	0.800	0.900	
mtddes	c· 0 99	0 0 93	6 0 82	8 0 67	6 0 50	0 0 32	4 0 1 7	2 0.06	4 0.010)

mtddesc: 0.990 0.936 0.828 0.676 0.500 0.324 0.172 0.064 0.010 Chance of MTD on de-escalation

The primary efficacy endpoint for Phase II is the rate of response by RECIST (CR, PR, SD, PD). The null hypothesis to be tested is that the RP2D observed in Phase I is not efficacious. We will use the standard Simon's two-stage design with 80% power at alpha level 0.05. The response rate is assumed to be 5% for the standard treatment and 20% for quinacrine in combination with capecitabine. The Phase II portion will first enroll 10 patients. The trial will be stopped if no patient responds to treatment. Otherwise, 19 additional patients will be enrolled for a total of 29 patients. The drug will be declared to have sufficient response rate if 4 or more subjects respond to treatment.

The other primary end point for Phase II is time to tumor progression, which will be analyzed by the Kaplan and Meier method.

Toxicity endpoint: If ever 5 of the initial cohort of 10 patients experience DLTs, or if ever 8 of the 29 total evaluable phase II patients do, the trial will be halted for excess toxicity and either dose adjusted or terminated. If the true chance of DLT is 33.3% the trial will be halted in this way with power 80.5%. If the true toxicity is at most 15%, the chance of termination in error is at most 6.3%.

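### The Phase II toxicity rule has no limit of 6 or 7 DLTs, so it cannot halt at patients 11 to 13 and halts slowly up to patient 20; intermediate limits would be a cheap, modest improvement.

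*Combined protocol and SAP*

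**What the plan says.** The toxicity paragraph of section 11.1 gives two numerical limits for Phase II: "If ever 5 of the initial cohort of 10 patients experience DLTs, or if ever 8 of the 29 total evaluable phase II patients". When either is reached, "the trial will be halted for excess toxicity and either dose adjusted or terminated".

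The limits follow the accrual stages of the efficacy design: "The Phase II portion will first enroll 10 patients", and if at least one of them responds, "19 additional patients will be enrolled for a total of 29 patients".

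Two operating characteristics are stated. For a toxic dose: "If the true chance of DLT is 33.3% the trial will be halted in this way with power 80.5" per cent. For a tolerable dose: "If the true toxicity is at most 15%, the chance of termination in error is at most 6.3" per cent.

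Both limits apply continuously, patient by patient, not only at two fixed looks. Section 12.2 adds a toxicity review by the data safety monitoring board about every three months. It is worded as optional, is advisory, and has no numerical boundary.

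**The concern.** The boundary is flat at 5 up to patient 10 and flat at 8 from patient 11 to patient 29. A trial that passes patient 10 has at most 4 DLTs, so it needs at least four more before the rule can act again. The earliest possible second halt is 8 DLTs in 14 patients. The rule is therefore silent at patients 11, 12 and 13 whatever happens, and nearly silent for some patients after that. As an illustration, 5 in 10 (50%) halts, while 4 in 10 followed by three DLTs in a row, 7 in 13 (54%), continues.

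What is at stake is when the stated power is earned, not whether it is reached. This matters somewhat more here because Phase I can be very small. Section 3.1 allows as few as three Phase I patients, and its chart lets the top dose be declared the MTD after one patient without a DLT. The section 11.1 table puts the chance of escalation on first entering a dose level at 0.847 for a 30% DLT rate, and the same outcomes at the top level lead to its being declared the MTD. A dose with substantial toxicity can therefore reach Phase II, where this rule is the only numerical safeguard at trial level.

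**Working it through.** **Inputs (all from section 11.1).** Limits: 5 DLTs within 10 patients, 8 within 29. DLT rates: p = 1/3 and p = 0.15. Stated results: 80.5% and 6.3%.

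**Method.** Let L(n) be the limit in force at patient n, and a(n,k) the probability of not having halted after n patients with k DLTs so far. Start from a(0,0) = 1.

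- Continue: a(n,k) = a(n-1,k)(1-p) + a(n-1,k-1)p, for k < L(n).
- Halt at patient n: h(n) = a(n-1, L(n)-1) p.
- Halted by patient n: the sum of h(1) to h(n).
- Expected patients treated: the sum over n = 0 to 28 of the probability of not having halted by n.

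**Step 1: reproduce the plan.** The recursion gives 0.8050 at p = 1/3 and 0.0626 at p = 0.15, matching the stated figures. The 8-in-29 limit alone gives 0.8014 and 0.0586, so the stated figures use both limits.

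**Step 2: when the plan halts at p = 1/3.**

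- By patient 10: P(at least 5 of 10) = 0.2131.
- Patients 11 to 13: nothing is added, because 4 + 3 = 7 < 8. The figure stays at 0.2131.
- Patient 14: P(exactly 4 of 10) = 0.2276, and four DLTs in a row add 0.2276 × (1/3)^4 = 0.0028, giving 0.2159.
- By patient 15: 22.5%. By patient 20: 38.6%. By patient 26: 68.8%. By patient 29: 80.5%.
- So 80.5 − 68.8 = 11.7% of trials halt only at patients 27 to 29.

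The 7-in-13 path (4 of 10, then three in a row) has probability 0.2276 × (1/3)^3 = 0.0084, or 0.8%.

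**Step 3: add intermediate limits.** The same recursion, keeping 5 in 10 and 8 in 29, with two illustrative pairs of windows:

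| | Plan | 6 in 14, 7 in 20 | 6 in 12, 7 in 15 |
|---|---|---|---|
| Halt at 15% | 6.26% | 6.69% | 6.29% |
| Halt at 20% | 21.65% | 22.47% | 21.71% |
| Halt at 25% | 45.02% | 45.95% | 45.09% |
| Halt at 33.3% | 80.5% | 81.0% | 80.5% |
| Halted by patient 15, at 33.3% | 22.5% | 33.7% | 28.1% |
| Halted by patient 20, at 33.3% | 38.6% | 54.4% | 39.5% |
| Halted by patient 20, at 40% | 62.3% | 76.6% | 63.2% |
| Expected patients, at 33.3% | 21.0 | 19.6 | 20.7 |
| Expected patients, at 40% | 17.0 | 15.6 | 16.7 |

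**Step 4: allow for the futility stop.** The plan's toxicity figures ignore the stop for no responders among the first 10. If response and DLT are assumed independent, the chance of that stop is 0.8^10 = 10.7% at a 20% response rate and 0.95^10 = 59.9% at 5%. At a 33.3% DLT rate, expected patients with 6 in 14 and 7 in 20 then fall from 19.8 to 18.6 (20% response) or from 14.2 to 13.7 (5% response).

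**The case against.** The strongest reply is that the plan contains no error. It states a continuous rule, its two figures reproduce exactly, and what remains is a preference for a differently shaped boundary. That stands: this is an improvement, not a correction.

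Several stronger readings are tempting and should not be drawn.

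- A reader might take 7 in 13 as the main failure. It is a 0.8% path at a 33.3% DLT rate and only illustrates the gap. Any count limit tolerates some high early proportions: 4 DLTs in the first 4 patients continues under the plan and under every option above.
- A reader might say that the plan keeps treating patients at a rate it calls too toxic. Section 11.1 uses 33.3% to state power and does not label it that way, and the Phase I chart in section 3.1 accepts 2 DLTs in 6 patients as an MTD.
- A reader might conclude that patients are unprotected between the limits. Section 5.1 has patient-level holds, reductions and removal, section 3.5 lists unacceptable adverse events as a reason to end treatment, and section 12.1 provides real-time review of serious events. These mitigate the gap, as does the board review, but none is a numerical boundary for the trial as a whole.

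Two further points stand. Halting by patient 20 is measured exactly where a 7-in-20 limit expires, so it shows that option at its best; expected patients treated is the fairer summary. And no single pair of windows is uniquely right.

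**Conclusion.** The concern holds as a cheap improvement. The stated 80.5% and 6.3% are correct, but without a limit of 6 or 7 the rule cannot act at patients 11 to 13. At a 33.3% DLT rate it has halted only 38.6% of trials by patient 20, less than half of its eventual power.

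The benefit of filling the gap is modest. With 6 in 14 and 7 in 20, about 1.35 fewer patients are treated per trial at 33.3%, or roughly 1.35 × 1/3 = 0.45 fewer DLTs. Once the futility stop is counted, the saving is about 1.2 patients at a 20% response rate and 0.5 at 5%.

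The figures assume independent DLTs with a constant probability and each outcome known before the next patient enters. The futility adjustment also assumes independence of response and DLT.

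**What to change.** In section 11.1 keep both existing limits and add limits of 6 and 7 DLTs between patients 11 and 20, with windows chosen by the sponsor's statistician. Restate the two operating characteristics for the rule chosen, and say whether they allow for the futility stop.

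Two choices show the trade-off. With 6 within 14 and 7 within 20, the restated figures are 81.0% and 6.7%; the cost is about 0.4 points of false-halt probability at 15%, and about 0.8 and 0.9 points more halting at 20% and 25%. With 6 within 12 and 7 within 15, the present 80.5% and 6.3% survive rounding, but less is gained.

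The change takes one sentence and, at most, two restated figures. It does not raise the maximum of 29. A halt can, however, lead to a dose adjustment, and section 11.2 allows a larger total after a dose reduction, so each extra false halt has some cost. What happens to the dose after a halt is outside this point.

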11.2 Sample Size/Accrual Rate

Sample size for Simon's two-stage Optimum design will be as large as 29 (if the study progresses to stage 2) as described in section 12.1. If the study requires a dose reduction after the first 6 patients have enrolled, the sample size may be as large as 35 (29 at a 100 mg daily dose of quinacrine plus 6 patients who were treated at a 100mg bid dose of quinacrine). The study is expected to accrue over two years.

Patient Replacement: If during the Phase I or phase II portion of the study a patient is lost to follow-up before the patient can be evaluated at least once clinically or radiologically, the patient will not be

evaluable for the primary endpoint and will be replaced. Patients that are taken off-treatment due to severe drug related toxicity will not be replaced. If a patient is lost to follow-up after at least one evaluation is completed the patient will not be replaced and will be considered a failure towards the primary endpoint.

11.3 Stratification factors

There are no stratification factors.

11.4 Analysis of Primary Endpoints

The intent-to-treat population will include all patients who have received at least one dose of both Capecitabine and quinacrine. The response rate and its 95% confidence interval will be estimated using the approach described by Koyama and Chen (71), which accounts for the interim futility analysis.

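### Section 11.4's primary population ignores dose and phase, so after the dose reduction foreseen in 11.2 the response estimate would mix two doses, and the plan does not say which patients the 4-responder rule counts

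*Combined protocol and SAP*

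**What the plan says.** Section 11.1 names the Phase II design and its error rates: "We will use the standard Simon's two-stage design with 80% power at alpha level 0.05". It then gives the two rates to be told apart: "The response rate is assumed to be 5% for the standard treatment and 20% for quinacrine in combination with capecitabine". On the first stage it reads: "The Phase II portion will first enroll 10 patients. The trial will be stopped if no patient responds to treatment". The second stage, if reached, is described so: "Otherwise, 19 additional patients will be enrolled for a total of 29 patients". One success rule is given: "The drug will be declared to have sufficient response rate if 4 or more subjects respond to treatment".

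The same section has a toxicity boundary (5 DLTs among the first 10 patients, or 8 among 29). If it is crossed, "the trial will be halted for excess toxicity and either dose adjusted or terminated".

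Section 11.2 allows for a dose reduction once 6 patients have been enrolled. The total may then reach 35, described as "29 at a 100 mg daily dose of quinacrine plus 6 patients who were treated at a 100mg bid dose of quinacrine".

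Section 11.4, headed Analysis of Primary Endpoints, defines the population: "The intent-to-treat population will include all patients who have received at least one dose of both Capecitabine and quinacrine". Its next sentence applies the Koyama-Chen method to the response rate and its 95% interval.

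No section gives a threshold for 35 patients, restarts the response count after a dose change, or limits the primary response analysis to patients at the final dose.

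**The concern.** The design has one response rate, one dose, two stages (10, then 29) and an absolute count as its success criterion. The 11.4 population depends on none of these. Once a dose has been reduced, it contains patients who started at different doses, and nothing in its wording removes Phase I patients either.

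Two things are at stake. The first is the estimate. A rate and interval meant to describe the recommended dose would describe a blend, with 6/35 = 17% of the patients from a dose no longer in use. The second is the decision. An absolute threshold of 4 is easier to reach with 35 patients than with 29. For example, 3 of 29 (10.3%) at the new dose fails on its own. One response among the 6 earlier patients makes it 4 of 35 (11.4%), which passes if all 35 are counted. The trial is open-label, so without a written rule the choice between the two counts could be made after the responses are known.

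**Working it through.** **Inputs** (all from 11.1 and 11.2): null rate 5%, target rate 20%, first stage 10 with a stop at 0 responders, total 29, success at 4 or more; after a reduction, 29 new patients plus 6 earlier ones.

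**Step 1. Reproduce the stated design.** With x responders among the first 10,

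P(success) = Σ (x = 1 to 10) P[Bin(10, p) = x] × P[Bin(19, p) ≥ 4 − x].

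At p = 0.05:
- x = 1: 0.31512 × 0.06655 = 0.02097
- x = 2: 0.07463 × 0.24529 = 0.01831
- x = 3: 0.01048 × 0.62265 = 0.00652
- x ≥ 4: 0.00103
- Sum: 0.0468

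At p = 0.20 the same formula gives 0.801. The plan's 5% level and 80% power are reproduced. A search over two-stage designs meeting both constraints returns this one as Simon's optimal design. These are also the operating characteristics after a dose reduction if only the 29 new patients are counted.

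**Step 2. Count all 35, with the threshold still 4 and 5% true response at both doses.** Let y be the responders among the 6 earlier patients: P(y = 0) = 0.7351, P(y = 1) = 0.2321, P(y = 2) = 0.0305, P(y ≥ 3) = 0.0022.

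*(a) Futility look on the 10 new patients only.* The chance of success given y is 0.0468, 0.1353, 0.2823 and 0.4013 for y = 0, 1, 2 and ≥ 3.

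0.7351 × 0.0468 + 0.2321 × 0.1353 + 0.0305 × 0.2823 + 0.0022 × 0.4013 ≈ 0.0753.

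Power at 20% at both doses becomes 0.857.

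*(b) Futility look pooled over the 6 and the 10.* Any responder among the 6 now passes the look, so the conditional chances for y = 0, 1, 2, 3 are 0.0468, 0.1751, 0.4292 and 0.7741, and 1 for y ≥ 4. The weighted sum is 0.0899.

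| Patients counted | Type I error at 5% |
|---|---|
| 29 at the new dose | 4.68% |
| 35, look on the new 10 | 7.5% |
| 35, pooled look | 9.0% |

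**Step 3. Scenarios with unequal rates.** The documents give no response rate by dose, so these are assumptions. Under (a), with 5% at the new dose, the chance of declaring success is 4.68% if the earlier dose responds at 0%, 10.7% if at 10%, and 17.5% if at 20%.

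**Step 4. Average over trials with and without a reduction.** The Step 2 figures are conditional on a reduction after 6 patients. If a reduction is independent of response, the overall error under (a) passes 5% once the chance of a reduction exceeds (0.0500 − 0.0468)/(0.0753 − 0.0468), about 11%.

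**The case against.** The best defence is that the restart is already implied. Section 11.1 ties the 4-responder rule to a total of 29. Section 11.2 plans a complete 29 at the lower dose and lists the 6 on top, which would have little purpose if the 6 counted toward the test. Koyama-Chen inference is built for the two-stage design, which also points to the 29. Section 11.4 defines a population, not a decision rule, and read to the letter it would admit Phase I patients too, which cannot be what 11.1 intends for a Phase II test.

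Most of this stands. A reader might infer that the 5% error rate is lost after a dose reduction. The documents do not support that, because nowhere do they apply the threshold of 4 to 35 patients. Three further inferences should also be resisted:

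- *That the 6 are Phase II patients removed from a dose by the toxicity boundary.* Section 11.2 neither labels their phase nor refers to that boundary. Six is also the largest number per dose level in Phase I (3.1), and the two doses named are both Phase I levels.
- *That the sample grows in response to efficacy data.* The triggers in the text are a dose reduction and DLT counts.
- *That the error is about 17%.* Simulating the toxicity boundary gives such a figure, but only with a 33.3% DLT rate, a restart after every halt and a mean of 16 earlier patients. That is not the 35-patient plan, and 11.1 allows termination instead of a dose change.

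The defence does not settle the estimate. Section 11.4 is the text that governs the primary analysis, it is explicit, and following it puts both doses into the rate and the interval. The restart, however natural, is not written.

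**Conclusion.** The point holds as a conflict between a population defined without regard to dose and a decision set that is left undefined. The estimation part follows directly from 11.4 and 11.2: after the foreseen reduction, the reported rate and interval would describe two doses and would not fit the 10/29 structure. The error-rate part is conditional. It is within the planned 5% if only the new 29 count and above it if all 35 do, so control depends on a choice the plan does not make.

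The size rests on 6 earlier patients, independent responses and the null rate at both doses. The unequal-rate results are illustrations only. If the 6 are Phase I patients, the pooling problem is the same, because 11.4 does not exclude that phase. If no dose is reduced, this route to pooling does not arise, although the missing phase restriction in 11.4 remains. The change should be made, but this is not a demonstrated failure of the design.

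**What to change.** In 11.4, limit the primary response population to Phase II patients who start treatment at the final RP2D. In 11.1 and 11.2, state that after a Phase II dose change the response count restarts at zero, so that the 0-of-10 stop, the 4-of-29 success rule, the estimate and the interval all use only patients started at the new dose. Section 11.2 should also say which phase the 6 patients belong to. Report patients started at an earlier dose separately and descriptively, and keep them in the safety tables.

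The cost is a few sentences. No patients are added, because 11.2 already provides 29 at the reduced dose. The downside is that responses at the earlier dose no longer help the primary result. Keeping all 35 and raising the threshold to 5 would also control the error (2.47%, with power 79.4%, futility look on the new 10 and equal rates at both doses), but the estimate would still mix doses, so the restriction is preferable.

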11.5 Analysis of Secondary Endpoints

• Progression-free survival will be displayed with a Kaplan-Meier curve and the median PFS will be reported with its 95% confidence interval.

• PK parameters (C max, T1/2, AUC of quinacrine) will be described using graphical display and summarized using summary statistics (e.g., mean, median, confidence intervals).

• Adverse events will be tabulated by type and grade.

12.0 DATA, SAFETY MONITORING PLAN

12.1 Monitoring Plan

FCCC ISRU will monitor the medical and study records of each participant accrued throughout the course of the study. In addition, the ISRU will collect and report data to the study Sponsor Investigator who will review these data on a regular basis at a rate dependent on subject accrual. All serious adverse events (SAEs) will be reviewed on a real time basis first by the study site PI and subsequently by the ISRU and Sponsor Investigator as applicable.

12.2 Data Safety Monitoring Board

Interim analysis of toxicity, outcome and ongoing scientific investigations may be performed at least every 3 months by the Fox Chase Cancer Center Data Safety Monitoring Board (FCCCDSMB). In this capacity the FCCCDSMB will serve as an advisory committee to the Sponsor Investigator. The FCCCDSMB will review those aspects of this trial that are outlined in the responsibilities section of the Data and Safety Monitoring Plan (DSMP). If the committee decides that changes should be made to this trial, it will make recommendations in writing to the Study Principal Investigator, the Associate Director of Clinical Research, and the Protocol Management Executive Committee, which, in turn, have the authority to approve or disapprove these recommendations. These changes will be discussed with the Sponsor Investigator before they are implemented. These changes may

include early termination of accrual. Other changes might include altering the accrual goals or changing the eligibility criteria for the trial.

